5 STUDY ENDPOINTS

5.1 Efficacy Endpoints

5.1.1 Primary Endpoint

Time to recovery through Day 60 visit

5.1.2 Key Secondary Endpoint

All-cause mortality at Day 60 visit

5.1.3 Supportive Secondary Endpoints

- All-cause mortality at Day 30 visit
- Proportion of patients requiring invasive mechanical ventilation or dying during the 60 days from the SFISD
- Proportion of patients requiring invasive mechanical ventilation during the 60 days from the SFISD
- Differences in outcomes as measured by an 8-point ordinal scale at Day 12
- Differences in outcomes as measured by an 8-point ordinal scale at Day 30
- Number of Days in the Hospital
- Number of Days in the ICU

The primary analyses of the efficacy endpoints will be based on the patients in the baseline imputed $\text{PaO}_2/\text{FiO}_2 \leq 200$ subgroup.

5.2 Safety Endpoints

- Vital signs measurements
- Laboratory measurements
- Concomitant medications
- Treatment-emergent adverse events (TEAEs) and serious adverse events (SAEs)

5.3 Pharmacokinetic Endpoint

Not applicable for this SAP.

5.4 Pharmacodynamic Endpoint

Not applicable for this SAP.

5.5 Health-economics Endpoint

Not applicable for this SAP.

6 ANALYSIS POPULATIONS

6.1 All-Subjects Analysis Set

The All-Subjects Analysis Set will contain information from all screened subjects, including those who did not meet the study entry criteria or did not receive a study treatment.

6.2 Efficacy Analysis Set

Efficacy analyses will be based on the ITT principle. The Efficacy Analysis Set will include data from all subjects randomly assigned to study treatment. All data will be included and no subjects excluded because of protocol violations. For the analysis of efficacy data, subjects will be included in the treatment group according to their randomly assigned treatment.

Unless otherwise noted, all efficacy analyses will be performed using the Efficacy Analysis Set of the baseline imputed $\text{PaO}_2/\text{FiO}_2 \leq 200$ subgroup. All Efficacy Tests data will be listed.

6.3 Safety Analysis Set

The Safety Analysis Set will include data from all subjects randomly assigned to study treatment who receive any amount of Auxora or Placebo. All data will be included and no subjects excluded because of protocol violations. For safety data analysis, subjects will be included in the treatment group according to the treatment they actually receive.

7 TIMINGS OF ANALYSES

7.1 Safety Review

After the first 50 patients were randomized in Part 2, an IDMC evaluated safety data from the study. The IDMC will make a suggestion whether to continue the study without changes, or consider terminating the study due to a safety issue. The IDMC will again review the safety data when 70 patients with a baseline imputed $\text{PaO}_2/\text{FiO}_2 \leq 200$ have completed the study, and finally when 200 patients with a baseline imputed $\text{PaO}_2/\text{FiO}_2 \leq 200$ are randomized in Part 2 of the study. Adhoc safety reviews can be requested by the IDMC or sponsor during the study.

7.2 Interim Sample Size Re-estimation and Futility Analysis

One unblinded interim sample size re-estimation was planned and was conducted by the IDMC when 70 patients in the baseline imputed $\text{PaO}_2/\text{FiO}_2 \leq 200$ subgroup had completed the study. No ongoing study patients were included in this sample size re-estimation procedure. The sample size was re-estimated based on the interim estimation of the treatment recovery rate. The interim estimation of the recovery rate was also used in the non-binding futility analysis.

7.3 Final Analysis

The final analysis will be conducted when all randomized patients, based on the planned or the re-estimated sample size, complete the study.

8 STATISTICAL ANALYSES

8.1 General Considerations

The statistical evaluation will be performed using SAS[®] Version 9.4 or later.

In general, descriptive statistical methods will be used to summarize the data from this study. Unless stated otherwise, the term “descriptive statistics” refers to number of patients (n), mean, median, standard deviation (SD), minimum and maximum for continuous data, and frequencies and percentages for categorical data. Safety and efficacy summaries will be performed on the efficacy and safety analysis sets, respectively.

8.1.1 Number of Digits to Report

Table 2 Number of Decimal Places (DP)

Statistic	Specification	Apply to
Minimum, maximum	Same number of DPs as the data provided in the datasets	All original, i.e., non-derived, data provided in the datasets
Mean, median, confidence intervals	One more DP than the raw data	All
SD, SE	Two more DP than the raw data	All
Percentages	1 DP	All
p-values	3 DP	All
Odds Ratio	2 DP	All
Hazard Ratio	3 DP	All

8.1.2 Significance Level and Confidence Interval

The statistical tests will be performed as two-sided with significance level of 5%. The confidence intervals will be determined with a confidence level of 95%.

8.1.3 Descriptive Statistics Values to Calculate

Where appropriate, variables will be summarized descriptively (frequency and percent will be summarized for categorical variables; mean, SD, median, minimum, and maximum will be presented for continuous variables) by strata, study visit, and by treatment group.

The denominator for the percentages will be the total number of subjects in the treatment group and Analysis Set being presented, unless otherwise specified (e.g., on some occasions, percentages may be calculated based on the total number of subjects with available data at a particular visit and/or time point).

8.1.4 Derived Variables

8.1.4.1 Definition(s) of Baseline(s)

Unless otherwise specified, the baseline values are the last available assessment before or at the SFISD. If multiple measurements are recorded on the same day, the last measurement recorded prior to the dose of study medication will be used as the baseline value. If these multiple measurements occur at the same time or time is not available, then the average of these measurements (for continuous data) or the worst among these measurements (for categorical data) will be considered as the baseline value. **Baseline imputed PaO₂/FiO₂ is the worst value in the 24 hours before screening.**

8.1.4.2 Study Time

For patients enrolled in the study, the first dose of study medication will be administered on study hour 0. The study time in hours for an event is defined as event date and time – date and time of SFISD. The study day is defined as event date – date of SFISD + 1 day.

8.1.4.3 Definition(s) of (Percent) Change from Baseline(s)

For numerical variables, change from baseline will be calculated as the post-baseline value minus the baseline value. If percent change from baseline is required, then percent change from baseline will be calculated as the change from baseline divided by the baseline value, multiplied by 100. If baseline value cannot be determined for a particular variable, the change from baseline and percent change from baseline will not be calculated.

8.1.4.4 Adverse Events

Treatment-emergent AEs (TEAEs) are defined as AEs that started or worsened in severity on or after the SFISD.

All adverse events will be coded from the reported term using the Medical Dictionary for Regulatory Activities (MedDRA) version 23.0 or the later version.

8.1.4.5 Concomitant Medications

All concomitant medications will be coded using the WHO drug dictionary (B3 WHO Drug Dictionary Enhanced – Sep 2019 or the later version).

8.1.4.6 Lab Values Below/above the Limit of Quantitation Deriving

The lab values below the limit of quantification (BLQ) are collected in the form like “< 2” in the clinical data base. In this case the numeric value of the lab is a missing value. The cut-off value ‘2’ will be used to impute the missing value for this case. Similarly, for the lab values above the limit of quantification, the cut-off value will be used for the numeric value of the lab. Local labs are used in this study and all lab parameters will be standardized to common SI units.

8.1.5 Missing Data

Missing data will not be imputed in the summary of safety endpoints at each time point. The missing data imputation methods for efficacy analyses are described in Section 8.

Imputation of missing or incomplete dates will be performed on AEs and concomitant medications (procedures) conservatively for determining the timing relative to the dose of study product unless otherwise specified. Partial or missing dates will be listed as recorded in the electronic case report form (eCRF).

8.1.6 Pooling of Sites

Data collected from all sites will be pooled together for the analysis.

8.2 Subject Disposition

The number of patients who enter screening will be summarized, and the percentage of these patients who fail to meet entry criteria will be reported for total subjects. Screen failures will be summarized in total and by each reason for screen failure.

Subject disposition will be summarized for patients’ completion status of study treatment, status of outcome/discharge, and corresponding discontinue reasons in tables for each treatment group and then total subjects. The data listing for subject discontinuation will be generated.

8.3 Demographic, Other Baseline Characteristics and Medication

8.3.1 Demographic and Baseline Characteristic

Patient demographic and baseline characteristics will be summarized by mean, SD, median, minimum, and maximum for continuous variables; and by counts and percentages for categorical variables. Summaries will be provided separately for each treatment group and then total subjects. The following subject demographic and baseline characteristic are summarized. The demographic variables consist of age, age category (18-39, 40-64, 65+), sex, ethnicity and race. Baseline characteristics include height, weight, body mass index (BMI), time from symptom onset to randomization in days, baseline scores on 8-point ordinal scale, baseline imputed PaO₂/FiO₂ and category (≤ 200 , ≥ 201), baseline d-dimer, baseline ferritin, and baseline CRP. Efficacy and Safety Analysis Sets will be used for the summaries.

Other baseline variables such as relevant medical history or other medically relevant criteria could also be included in the baseline tables.

The 8-point ordinal scale is defined as:

Scale	Description
1	Death
2	Hospitalized, requiring invasive mechanical ventilation or ECMO
3	Hospitalized, requiring noninvasive mechanical ventilation or high flow supplemental oxygen
4	Hospitalized, requiring low flow supplemental oxygen
5	Hospitalized, not requiring supplemental oxygen but requiring ongoing medical care
6	Hospitalized, not requiring supplemental oxygen or ongoing medical care
7	Discharged, requiring supplemental oxygen
8	Discharged, not requiring supplemental oxygen

8.3.2 Comorbidity

A summary table of the number and percentage of patients by the category of comorbidity will be produced for patients in the Efficacy Analysis Set. The summary will be provided by treatment groups and then by total treatment groups. Comorbidity will be sorted alphabetically by categories of comorbidity. The number and percentage of patients with none, one and two or more categories of comorbidities will also be summarized. Listings for comorbidity will also be provided.

8.3.3 Concomitant Medications

Concomitant medication is defined as any medication, other than study medication, which is taken on or after the start day of treatment. The concomitant medication data will be coded using World Health Organization Drug Dictionary (B3 WHO Drug DDE – Sep 2019 or the later version). The number and percentage of subjects taking concomitant medications will be summarized overall and by ATC level 2 terms, preferred drug names and treatment groups. A separate listing for concomitant medications will also be provided.

Concomitant Medications of Vasopressors, Corticosteroids, Antivirals And Anticoagulants for COVID-19 Newly Started on or After Day 1 of Study Treatment will be summarized by treatment group.

8.4 Primary Endpoint Analysis

8.4.1 Definition of Endpoint

Time to recovery through the Day 60 visit in the 8-point ordinal scale is the primary endpoint.

The primary estimand corresponding to the primary endpoint is defined as:

1. Treatment: 2.0 mg/kg (1.25 mL/kg) of Auxora administered at 0 hour and 1.6 mg/kg (1 mL/kg) administered at both 24 hours and 48 hours from the Start of the First Infusion of Auxora with local standard of care.
2. Population: Severe COVID-19 pneumonia patients with a baseline imputed $\text{PaO}_2/\text{FiO}_2 \leq 200$.
3. Variable: Time to recovery defined as time from SFISD to the first time a patient achieves the scale of 6, 7 or 8 on the 8-point ordinal scale for at least 24 hours.
4. Population level summary: Median difference using Kaplan-Meier estimate

Intercurrent events under consideration: 1) prohibited immunosuppressive medications or immunotherapies. 2) convalescent plasma treatment, 3) treatment discontinuation and 4) death.

The null and alternative hypotheses are:

- Null hypothesis H_0 : Time to recovery curves are the same between the two treatment arms
- Alternative hypothesis H_1 : Time to recovery are different between the two treatment arms

8.4.2 Main Analytical Approach

Time to recovery through Day 60 visit will be displayed using a Kaplan-Meier estimate and will be compared between the 2 treatment groups using stratified log-rank test stratified by baseline imputed $\text{PaO}_2/\text{FiO}_2$ screening of ≤ 100 vs. > 100 . Prohibited immunosuppressive medications or immunotherapies, convalescent plasma treatment and treatment discontinuation will be ignored (treatment policy strategy). Death will be treated as not recovered and time to recovery will be censored at Day 65 (composite strategy). Patients, including withdrawal of consent patients, will be censored at the last ordinal scale assessment if no recovery event is observed during the study (administrative censoring). The trial level Type I error of 0.05 between the two tests of the primary endpoint analysis and the key secondary endpoint analysis is controlled using the Benjamini and Hochberg method.

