- Draw blood samples for daily laboratory monitoring. Daily laboratory monitoring may be performed on blood drawn in the previous 12 hours
- Draw blood samples for every 72-hour laboratory monitoring at 216 hours. 72-hour laboratory monitoring may be performed on blood drawn in the previous 12 hours

8.10 Days 12 to 28

For patients who remain hospitalized 12, 14, 16, 18, 20, 22, 24, 26, and 28 days (±4 hours) from the SFISD:

- Record concomitant medications
- Record vital signs
- Record the lowest SpO₂ in the previous 24 hours and the time it was performed. The FiO₂ at the time of the SpO₂ measurement will also be recorded
- Record the SpO₂ and the FiO₂ at the time of the assessment
- Record ABG and time drawn if performed as part of standard of care
- Complete Daily Assessment Ordinal Scale
- Perform AE/SAE assessment

Patients discharged prior to Day 12 with the need for supplemental oxygen will be contacted on Day 12 to determine if they are still receiving supplemental oxygen.

8.11 Day 60 and Day 30

Patients who have been discharged from the hospital before Day 25, will be followed-up on Day $30 \ (\pm 5 \ days)$ for an AE/SAE assessment as well as to determine if they are receiving supplemental oxygen. For patients discharged from the hospital on Days 25-29, the final inpatient safety assessment will substitute for the Day 30 safety and mortality assessment. The Day 30 safety and mortality assessment may be conducted with an HCP.

Patients, who have been discharged from the hospital before Day 55, will be contacted on Day $60 \ (\pm 5 \ days)$ to determine if they are receiving supplemental oxygen, experienced any symptoms suggestive of long COVID, and developed any SAEs since the Day 30 assessment. The Day 60 assessment will be completed as a final inpatient safety assessment for patients who remain hospitalized or are discharged from the hospital on Days 55-59.

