8.12 Discharge Date

The time and date of initial discharge will be recorded, any re-admission and subsequent discharge date, as well as if the patient was sent home on oxygen when discharged, and if the patient was sent to a nursing home.

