8.13 Study Assessments

The Daily Assessment-Ordinal Scale will be filled out daily for all patients.

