10.8 Efficacy Analysis

Efficacy analyses will be presented by treatment group (Auxora vs Placebo) based on the Efficacy Analysis Set of the imputed $PaO_2/FiO_2 \le 200$ subgroup, except where it is specified otherwise. This section describes the analyses conducted at the final analysis time point when all randomized patients (based on the planned or the re-estimated sample size) have completed or discontinued from the study, assuming that the study is continued after IDMC reviews.

Recovery is defined as satisfying categories 6, 7, or 8 on the 8-point ordinal scale:

- Hospitalized, not requiring supplemental oxygen or ongoing medical care
- Discharged, requiring supplemental oxygen
- Discharged, not requiring supplemental oxygen

The 8-point ordinal scale is defined as

- 1. Death
- 2. Hospitalized, requiring invasive mechanical ventilation or Extracorporeal Membrane Oxygenation (ECMO)
- 3. Hospitalized, requiring non-invasive ventilation or high flow supplemental oxygen
- 4. Hospitalized, requiring low flow supplemental oxygen
- 5. Hospitalized, not requiring supplemental oxygen but requiring ongoing medical care
- 6. Hospitalized, not requiring supplemental oxygen or ongoing medical care
- 7. Discharged, requiring supplemental oxygen
- 8. Discharged, not requiring supplemental oxygen

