10.8.1 Primary Efficacy Analysis

Time to recovery of the imputed $PaO_2/FiO_2 \le 200$ subgroup is the primary endpoint and is defined as the number of days from the SFISD to the date of recovery. Failure to recovery and death are both censored at Day 61.

Time to recovery will be displayed using a Kaplan-Meier estimate and will be compared between the 2 treatment groups using a stratified log-rank test stratified by the baseline imputed PaO2/FiO2 of ≤100 vs. >100 with an overall 2 sided alpha level of 0.05 using the Benjamini and Hochberg method.

In addition, the recovery rate ratio and the 95% CI will be estimated using a Cox proportional-hazard model with treatment as the independent variable.

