8.4.3 Sensitivity Analyses

There are three planned sensitivity analyses that target the primary estimand. The first will be to relax the assumption that the baseline imputed $\text{PaO}_2/\text{FiO}_2$ is a confounding factor, so the analysis will be repeated but without stratification by the baseline imputed $\text{PaO}_2/\text{FiO}_2$ of ≤ 100 vs. > 100 . This analysis implies the baseline risk is the same across strata.

The second sensitivity analysis is based on a different administrative censoring rule and same analysis as the main analysis will be performed. Patients will be censored at the last ordinal scale assessment before or on the outcome visit if no recovery event is observed before or on the

outcome visit. This is to address the data collection limitation between the Day 30 outcome visit and Day 60 visit assessment related to the assessment of the primary endpoint.

The third sensitivity analysis is based on a different censoring rule for the prohibited immunosuppressive medications or immunotherapies and convalescent plasma treatment. In this sensitivity analysis, all data after the prohibited immunosuppressive medications or immunotherapies and convalescent plasma treatment will be excluded from the analysis. The time to recovery will be censored at the beginning of the prohibited immunosuppressive medications or immunotherapies or convalescent plasma treatment.

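### The SAP and protocol censor living non-recovered patients differently in the primary log-rank test, and the SAP rule may let later outcome decide who is censored

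*SAP*

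**What the plan says.** Protocol 10.8.1 has one rule for everyone who does not recover: "Failure to recovery and death are both censored at Day 61".

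SAP 8.4.2 splits them. For deaths: "Death will be treated as not recovered and time to recovery will be censored at Day 65 (composite strategy"). For everyone else: "Patients, including withdrawal of consent patients, will be censored at the last ordinal scale assessment if no recovery event is observed during the study". The SAP describes itself as based on protocol version 8.1 and does not mention the change.

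When the last ordinal assessment falls is not fixed:

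- Protocol 8.10 lists the scale at visits "For patients who remain hospitalized 12, 14, 16, 18, 20, 22, 24, 26, and 28 days". Section 8.11 does not list it at Day 30 or Day 60, and Appendix 2 has no mark for it in that column.
- Protocol 8.13 has no end day: "The Daily Assessment-Ordinal Scale will be filled out daily for all patients".
- Protocol 3.1 has inpatient assessments every 48 hours to Day 30, and a Day 30 ordinal endpoint is analysed.

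Discharge dates also carry no end day (Protocol 8.12): "The time and date of initial discharge will be recorded". Protocol 10.8 makes discharge a recovery: "Recovery is defined as satisfying categories 6, 7, or 8 on the 8-point ordinal scale", where 7 and 8 are the discharged categories. SAP 5.1.1 runs the endpoint through the Day 60 visit. Neither document says whether a recovery between Day 28 and Day 60 is read from a form or from the discharge record.

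SAP 8.4.3 adds a second sensitivity analysis that censors at the outcome visit, and explains: "This is to address the data collection limitation between the Day 30 outcome visit and Day 60 visit assessment".

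**The concern.** Two governing documents give different censoring rules for the confirmatory test, and the difference is not confined to missing data. A patient seen in hospital and not recovered at Day 60 has a known outcome, yet the SAP censors that patient at whatever day the last form was completed.

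If forms stop near Day 28 but later discharges count, a patient discharged on Day 40 stays at risk and becomes an event, while a patient still on oxygen in hospital at Day 60 is removed at Day 28. Exit at Day 28 is then decided by what happens afterwards. Deaths stay in to Day 65, so after Day 28 the risk set holds only future recoverers and the dead.

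Two things follow. Late Kaplan-Meier recovery is overstated in both arms. And the log-rank statistic moves toward the arm with fewer deaths and more long-stay survivors, even when recovery is the same in both. Day 60 mortality is the key secondary endpoint, so a difference in the death share is a possibility the trial is designed to look for.

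**Working it through.** **The plan's own figures.** Schoenfeld events for ratio 1.43, two-sided 0.05, 90% power, 1:1: 4(1.960 + 1.282)²/(ln 1.43)² = 42.04/0.3577² ≈ 329, against 330 stated. Protocol Table 6 pairs 320 patients with 266 events (266/320 = 83%). Power at ratio 1.49 is Φ(½√266 × ln 1.49 − 1.96) = Φ(3.252 − 1.960) = 0.902, so the stated 90% reproduces. The censoring question does not alter these.

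**The rules side by side** (day of event or censoring)

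| Patient | Protocol | SAP, forms to Day 28 | SAP, forms to Day 60 |
|---|---|---|---|
| Discharged Day 40 | event, 40 | event, 40 | event, 40 |
| Dies unrecovered | 61 | 65 | 65 |
| Alive, unrecovered at Day 60 | 61 | 28 | 60 |

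Only the last row matters. With no recovery after Day 60, Day 61 against Day 65 changes nothing.

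**Kaplan-Meier.** Let E be the share recovered by Day 28, L recovered later, D dead, S alive and not recovered. The protocol rule gives E + L at Day 60. The SAP rule with forms to Day 28 removes S at Day 28 and gives 1 − (1 − E) × D/(L + D).

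Assume E = 0.79 and L = 0.04 in both arms (true recovery 83%):

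- Placebo, D = 0.14, S = 0.03: 1 − 0.21 × 0.14/0.18 = 0.837
- Auxora, D = 0.07, S = 0.10: 1 − 0.21 × 0.07/0.11 = 0.866

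**Log-rank, same case, 160 per arm.** The rules agree to Day 28, so any shift comes from late events. After Day 28, 160 × 0.11 = 17.6 Auxora and 160 × 0.18 = 28.8 Placebo patients are at risk, with 6.4 late recoveries in each arm. Halfway through these, the Auxora share at risk is (17.6 − 3.2)/(46.4 − 6.4) = 0.36.

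- U ≈ 6.4 − 12.8 × 0.36 = 1.79
- V ≈ 252.8/4 + 12.8 × 0.36 × 0.64 = 66.1
- Z shift ≈ 1.79/√66.1 = 0.22; ratio ≈ exp(1.79/66.1) = 1.03

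Under the protocol rule both arms have 21% at risk after Day 28, and the expected U is 0.

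**Simulation.** 160 per arm, 10,000 runs, unstratified log-rank, identical true recovery. Early recoveries are rounded log-normal (median parameter 9 days, limited to Days 2–28); late ones are uniform on Days 31–60. All outcome rates are assumptions; only the 83% total comes from the design. Favourable rejections are nominally 2.5%.

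| Recovered | of which late | Deaths, Placebo v Auxora | Z shift | Ratio | Favourable rejections, SAP v protocol |
|---|---|---|---|---|---|
| 83% | 4% | 12% v 9% | 0.10 | 1.01 | 3.1% v 2.5% |
| 83% | 4% | 14% v 7% | 0.22 | 1.03 | 4.5% v 2.7% |
| 83% | 8% | 14% v 7% | 0.40 | 1.05 | 6.1% v 2.7% |
| 83% | 4% | 7% v 14% | −0.23 | – | 1.3% v 2.5% |
| 74% | 4% | 20% v 10% | 0.25 | – | 4.3% v 2.6% |
| 78% | 8% | 18% v 6% | 0.63 | – | 8.4% v 2.3% |

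In the second row the simulated Day 60 Kaplan-Meier values are 83.6% and 86.7%, in line with the formula.

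**Checks**

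- Identical arms: two-sided rejection 4.8% (SAP) against 4.9% (protocol).
- Forms to Day 60: identical to the protocol rule.
- Second sensitivity analysis, or late recoveries not counted: absolute Z shift at most 0.005.
- Kaplan-Meier medians: unchanged in every run.

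A second set of assumptions (75% recovered by Day 28, 8% on Days 29–60, 6,000 runs) gives two-sided rejection of 5.9% against 5.0% for deaths of 15% v 10%, and 8.6% against 4.7% for 15% v 5%. With 2% late and deaths 15% v 5% it is 5.8% against 5.6%.

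**The case against.** The bias needs two things at once: ordinal status ending near Day 28, and later discharges still counting. Neither is established. Protocol 8.13 has the scale completed daily with no stop, a Day 30 ordinal endpoint is planned, and SAP 8.4.1 defines recovery on the scale itself. If events and censoring both come from that one source, exit does not depend on later outcome. The wording of the second sensitivity analysis also reads naturally as though ordinal status can exist after the outcome visit. This stands, and it is why the bias is put conditionally. It does not remove the contradiction between the documents.

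The SAP already recognises the Day 30 to Day 60 data gap, and its second sensitivity analysis removes the shift. True, but that is not the confirmatory test.

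The estimand's summary measure is the difference in medians, which does not move. Also true, but the p-value comes from the log-rank test, which does.

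The size depends on chosen inputs. The sample-size text gives a study length of 60 days in the synopsis but 30 days in Protocol 10.2 and SAP 4; on the 30-day reading the design implies no late recoveries. With only 1–2% late, the Z shift is 0.03–0.05 for deaths of 12% v 9%, and 0.06–0.12 for 14% v 7%. Every non-null case also assumes that fewer deaths mean more patients alive but still not recovered at Day 60, which no document supports or rules out.

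Protocol 10.1 lets the SAP add missing-data detail, and the SAP's handling of withdrawals fills a gap in the protocol. That part should be kept. Known non-recovery is not missing data.

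**Conclusion.** The point holds. The conflict over living non-recovered patients is plain on the text, affects the confirmatory primary test, is not flagged, and is not covered by any planned analysis that restores the protocol rule.

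The bias is real if forms stop near Day 28 and later discharges count, and practically absent otherwise. Under that reading, with 83% recovery and 4–8% of patients recovering late, a 3- to 7-point difference in deaths moves Z by about 0.1 to 0.4 and favourable rejections from about 2.5–2.7% to 3.1–6.1%. It is smaller when late recoveries are rare and can reach 0.63 in a harsher case. It can favour or penalise Auxora. Type I error is not inflated when the arms are identical, and medians reached before Day 28 are unaffected. This should be fixed; it does not by itself invalidate the design.

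**What to change.** 1. In SAP 8.4.2, censor deaths and all patients known not to have reached category 6, 7 or 8 by the Day 60 assessment at one common day at the end of the window: Day 61 as in the protocol, or Day 65 to cover the visit window. Put the same day in Protocol 10.8.1.
2. Take Day 60 status from the ordinal category, not from hospitalisation alone, because category 6 is an inpatient category that counts as recovery.
3. Reserve last-assessment censoring for patients whose later status is truly unknown: withdrawal of consent, loss to follow-up, and surviving patients with a new Do Not Intubate order, who under Protocol 6.2 have mortality follow-up only.
4. Name one source, form or discharge record, for status from Day 28 to Day 60, and use it for recovery and non-recovery alike.
5. Reconcile Protocol 8.13 with 8.10 and Appendix 2 on when the scale ends.
6. Keep the current SAP rule as a sensitivity analysis.

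The cost is mainly wording in both documents; sample size and event counts do not change, and discharge and readmission dates are already recorded. If forms did stop at Day 28, the Day 60 category of patients still in hospital must be taken from inpatient records, which is a modest retrieval task.
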